# Secondary outcome measures and assessment points

The secondary outcome of this study is to determine if the effect of PPT-S+ on smoking outcome is mediated by greater use of PPT-consistent strategies, reduced attraction to smoking, or greater smoking cessation self-efficacy. Participants will complete a Treatment Strategies Questionnaire at sessions 4-6 to assess frequency of general smoking cessation strategies usage, including planning for high-risk situations, and PPT-consistent strategies. PPT-consistent strategies are worded in a general way so that participants in each condition can rate how often they have done that activity; PPT-S consistent strategies include intentionally focusing on mental health benefits of quitting, using signature strengths, savoring positive experiences, and engaging in positive social interactions [2]. For those in PPT-S+, we also will have a record of how many PPT-S+ interactive texts were responded to, which will be coded according to whether the exercise was completed. In both conditions, we will calculate a variable reflecting the percent of responses to interactive messages. Smoking cessation self-efficacy will be measured at each counseling session using a well-validated 9-item scale [7]. Residual attraction to smoking (e.g., "Does smoking have any attraction for you now?") will be assessed at the end of the treatment (i.e. 4 weeks after quite date) with a validated 3-item scale [8].

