Study Analysis Plan

Positive Psychotherapy for Smoking Cessation Enhanced With Text Messaging: A Randomized

Controlled Trial

NCT02997657

December 22, 2022

[name]., Principal Investigator

Analysis Plan

Initial analyses will use chi-square tests to examine group differences in biochemicallyvalidated, 7-day point prevalence smoking abstinence at each follow-up as well as continuous abstinence across follow-ups. The primary outcome analysis will utilize Generalized Estimating Equations [1, 2] to test the effect of treatment condition on abstinence at 12, 26, and 52 weeks post quit date. GEE is a method of repeated measures analyses for categorical and continuous outcomes that allows for appropriate modeling of covariance structures when observations are correlated across time [3]. The primary, between groups, independent variable in the analysis is treatment group assignment. ST+ will be used as the reference group in this model. The model will contain a linear effect of time as well as the variables included in the urn randomization gender, cigarette dependence, and CES-D PA—following clinical trial analysis recommendations [4]. A second step will test the interaction between treatment condition and time to determine whether relative effects of PPTS+ change over time.

We will also determine if intervention engagement, reduced attraction to smoking, or greater self-efficacy mediates the relationship between PPT-S+ and smoking behavior. A regression analysis will be performed predicting the mediators at session 6 (note that the self-report measures assess strategies used during the quit attempt retrospectively, while attraction and self-efficacy refer to the current moment). Additionally, we will run a second model which adds the mediators to the main effects generalized estimating equations model testing outlined in the previous paragraph. We will use the asymmetric products of coefficients method to calculate the significance of this indirect effect and its 95% confidence interval using the RMediate program [5, 6]. Mediators will be tested sequentially such that strategies will be entered first followed by reduced attraction to smoking and self-efficacy, which serve as more proximal mediators. Follow-up analyses will examine individually each of the four core PPT-S strategies to isolate whether either of these are more important to outcomes.

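### The session-6 mediation model adjusts for neither smoking since the quit date nor earlier self-efficacy, so a mediator that treatment moves can test as significant without affecting abstinence

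*SAP*

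**What the plan says.** The SAP (Analysis Plan, mediation paragraph) builds the test from two models. For the treatment-to-mediator path: "A regression analysis will be performed predicting the mediators at session 6". No covariates are listed for it. For the mediator-to-abstinence path: "we will run a second model which adds the mediators to the main effects generalized estimating equations model testing". That main-effects GEE tests arm, and "The model will contain a linear effect of time as well as the variables included in the urn randomization": gender, cigarette dependence and CES-D PA. The product of the two paths gets an asymmetric 95% interval. On order of entry: "Mediators will be tested sequentially such that strategies will be entered first followed by reduced attraction to smoking and self-efficacy". The SAP then plans: "Follow-up analyses will examine individually each of the four core PPT-S strategies".

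The SAP also notes what the scores describe. Strategy items look back over the quit attempt, whereas attraction and self-efficacy are the participant's state when rated.

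The Protocol (Behavioral Treatment Conditions) sets six weekly sessions with the quit date at session 3, two weeks after the first. Under Secondary outcome measures it says "Participants will complete a Treatment Strategies Questionnaire at sessions 4-6" and "Smoking cessation self-efficacy will be measured at each counseling session using a well-validated 9-item scale"; attraction is planned once only. Under Primary outcome measures it plans Timeline Followback, and expired CO at every treatment session. Neither document puts early smoking or earlier self-efficacy into a mediation model, and neither plans a sensitivity analysis for mediator-outcome confounding.

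**The concern.** Randomisation protects the arm-to-mediator path. It does not protect the mediator-to-abstinence path, which compares participants who ended treatment with different mediator scores. By session 6 some participants will have stayed quit and some may have relapsed; the Protocol expects this, since it allows a new quit date after relapse and covers slips in sessions 4 to 6. If staying quit raises self-efficacy or lowers attraction, and also predicts abstinence at weeks 12 to 52, the mediator coefficient absorbs part of that link. A stable trait behind both self-efficacy and later abstinence does the same. The adjusting variables are baseline measures and cannot stand in for smoking after the quit date.

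A biased mediator coefficient becomes a false indirect effect only if treatment also moves the mediator. That is expected for strategies, which PPT-S+ trains. The Protocol (PPT-S+) hypothesises it for self-efficacy and the attractiveness of smoking.

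Mediation is the Protocol's stated secondary outcome. From the planned model alone, a reader cannot separate a mediator that kept people abstinent from one that rose because they were abstinent.

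**Working it through.** **Timing.** Session 6 is (6 − 1) × 1 = 5 weeks after session 1, and the quit date is 2 weeks after it. The mediators are therefore rated 5 − 2 = 3 weeks into the quit attempt.

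**The plan's own figures.** The documents give no power or error rate for the mediation test. The nearest figure that can be checked is the 298 for continuous abstinence (20% vs 8%, power .80). With a pooled proportion of .14 and two-sided 5%, n per arm = [1.960·√(2·.14·.86) + 0.842·√(.20·.80 + .08·.92)]² / .12² = 130.1, rounded up to 131 (262 in total). The continuity correction gives 147 per arm, 294 in total, close to 298. The simulations use 340 × 0.90 = 306. This assumes that everyone not lost has session-6 scores; attendance is not given.

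**Size of the bias.** Let the mediator have no effect on abstinence. Early abstainers (50%) score g SD higher, and early abstinence has odds ratio OR for later abstinence. The mediator's apparent log-odds per SD is then roughly ln(OR) × (g/4) / (1 + g²/4).

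- g = 0.25, OR 3: 1.099 × 0.0615 = 0.068, apparent OR 1.07 (simulated 1.07)
- g = 0.5, OR 5: 1.609 × 0.1176 = 0.189, apparent OR 1.21 (simulated 1.19)
- g = 0.8, OR 5: 1.609 × 0.1724 = 0.277, apparent OR 1.32 (simulated 1.29)

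**Simulated false indirect effects.** There were 1,000 trials per row. Abstinence was set to the Protocol's assumed rates (30/17.5/12.5% and 45/30/25%), except where session-1 self-efficacy also predicts abstinence. The outcome model was a logistic GEE with independence working correlation and robust errors, tested by a 95% product interval. Early smoking was added to the outcome model only; session-1 self-efficacy was added to both models. The arm effect on the mediator is 0.4 SD unless stated. All of g, OR and the arm effect are assumptions.

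| Assumed situation | Planned | + early smoking | + early smoking and session-1 self-efficacy |
|---|---|---|---|
| No confounding | 4.9% | 4.9% | 3.9% |
| g 0.25, OR 3 | 9.0% | 5.8% | 5.2% |
| g 0.5, OR 3 | 22.0% | 4.9% | 4.5% |
| g 0.5, OR 5 | 40.5% | 5.2% | 4.3% |
| g 0.8, OR 5 | 71.8% | 4.5% | 4.2% |
| g 0.8, OR 10 | 86.6% | 4.5% | 4.7% |
| No arm effect on mediator, g 0.5, OR 5 | 2.3% | 0.0% | 0.1% |
| Arm acts only via early abstinence (40% vs 55%), g 0.8, OR 5 | 11.9% | 0.5% | 0.4% |
| Session-1 self-efficacy predicts abstinence (OR 1.4 per SD), g 0 | 34.7% | 34.3% | 5.4% |
| The same, plus g 0.5, OR 5 | 83.0% | 35.3% | 4.5% |

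**A second simulation** let PA and dependence also drive early abstinence, later abstinence and, for PA, the mediator, so that the planned covariates had work to do. With an arm effect of 0.5 SD and gaps of 0 / 0.2 / 0.4 / 0.6 SD, false indirect effects were 5 / 16 / 49 / 86% when early abstinence strongly predicted week 12 (60% vs 15%), and 4 / 9 / 21 / 34% when weakly (50% vs 25%). Adding early smoking gave 4–7%, or 5–16% if 10–20% of early smokers report abstinence (gaps 0.4–0.6 SD). The planned covariates do not remove the problem.

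**What adjustment can destroy.** In the same framework, when strategies truly work but only through early abstinence, the smoking-adjusted session-6 model detects the effect in 0–3% of trials. With an unmeasured common cause of early and later smoking, it is significant in the wrong direction in 14–43%.

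**The case against.** The strongest defence is that early abstinence may be the route by which the mediators work. The Protocol describes self-efficacy as a possible predictor of immediate as well as long-term outcome. Conditioning on early smoking would then remove a real effect or open collider bias, as the last figures above show. This stands. A reader might infer that the planned model is simply wrong and should be replaced; the documents do not support that, and leaving early smoking out of the main model is defensible.

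Second, strategy scores look back over the whole quit attempt, so smoking in that window may follow from strategy use rather than precede it. This also stands. The confounding argument is clearest for self-efficacy and attraction. For strategies the direction is ambiguous, so the large figures show what one direction would do, not what happened.

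Third, the Protocol says "PPT-S consistent strategies include intentionally focusing on mental health benefits of quitting". A reader might infer that this strategy, being tied to having quit, would come out first of the four even if none works. That needs an arm effect on it as large as on the others. Table 1 lists benefits of quitting among the smoking cessation components, and the Standard Treatment+ section says both arms receive that content, so its arm contrast may be the smallest. With none of the four effective and an equal 0.5 SD arm effect, it tests as significant in 19–78% of simulated trials. With 0.25 SD on it and 0.5 SD on the others, this falls to 8–37%, and it ranks first on the indirect effect in 25–47%. At 0.1 SD the figures are 2–10% and 12–24%, against 25% by chance. The ranking claim should not be made.

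Fourth, no confounding strength comes from the documents. That limits the claim to direction and range, but does not remove it.

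**Conclusion.** The omission is plain in the SAP, and the direction of the consequence follows from the design: where treatment moves the mediator, the planned test can declare an indirect effect for a mediator that does nothing. Its size cannot be fixed from the documents. Over the assumed strengths the false-positive rate runs from about 5% to over 80%. It stays near or below 5% if treatment does not move the mediator and early abstinence is similar in both arms. If early abstinence differs between arms, some excess can arise without a direct effect (11.9% in the row above).

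This is a limit on interpretation that inexpensive additions can address. A reader might infer that any mediation finding will be false, or that the efficacy result is in doubt. Neither follows: the primary GEE contains no mediator, and the planned mediation result may be correct.

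A separate, minor point is that the Protocol (Secondary outcome measures) places residual attraction 4 weeks after the quit date, while the session schedule and the SAP's session-6 analysis imply about 3.

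**What to change.** 1. Adjust self-efficacy for its session-1 value in both the mediator regression and the outcome GEE, provided that score was taken before the allocation folder was opened and counselling began. The folder is opened at session 1 and PPT-S+ content starts there, and the documents do not give the order, so the study team must confirm it. Attraction has no earlier value to use.
2. Keep the planned session-6 model as the main one. Beside it, report a sensitivity GEE that adds smoking status from the quit date to session 6 to the outcome model only, not to the mediator regression. Use session CO where available, otherwise Timeline Followback. Do the same for the single-strategy analyses, without claims about which strategy ranks first.
3. Do not use the adjusted model as a pass/fail gate. State that the planned result may reflect early abstinence driving the mediator, that the adjusted result may remove a real effect working through early abstinence or carry collider bias, and that disagreement is inconclusive about mechanism.
4. Label these additions post hoc if the mediation analysis has already been run. Follow-ups were due by December 2021 and the SAP is dated December 22, 2022.
5. Reconcile the 3-week and 4-week timing of attraction.

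The cost is SAP wording and a few extra model runs on measures already planned. Session CO is probably missing for remote sessions after March 2020. Cotinine cannot replace it, because session 6 falls within the eight-week patch supply, so those participants rest on self-report. The adjusted model has little power for effects that work through early abstinence.

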The PPT-S+ model acknowledges that PPT-S+ may directly enhance positive affect, given prior research on positive psychology interventions. It also acknowledges that individuals with greater positive affect may find it easier to engage in PPT-S+ strategies. In our pilot trial, the effect of PPT-S was, in fact, stronger among those with higher levels of positive affect prior to treatment[19]. However, results also suggested that it was use of PPT-S strategies that was more predictive of long-term outcome than positive affect itself.

The following intervention elements are unique to PPT-S+ (see Table 1 for timing of interventions):

PPT-S Model of Smoking Cessation. PPT-S+ highlights that despite initial withdrawal symptoms, quitting smoking results in improved mental health and reduced stress [17, 19, 28-31]. The importance of attending to positive experiences and having positive social interactions when quitting is emphasized, noting that these experiences help people manage future obstacles. Counselors note that the exercises taught in PPT-S+ can be more difficult to complete during periods of stress or low mood, but that regular practice of the exercises has been shown to increase satisfaction with life and positive moods and reduce depression.

Positive Introductions. PPT-S+ begins by introducing the concept of signature strengths and how those can be important in quitting smoking. Participants are provided feedback about their top five signature strengths based on the Values in Actions Survey [32], which assesses 24 signature personality strengths such as *Love of Learning*, *Kindness*, *Appreciation of Beauty*, and *Gratitude*. Participants are asked to share how they have demonstrated use of one of these strengths in a recent situation.

Using Signature Strengths. Counselors highlight the role that signature strengths play in leading an engaged life and handling challenges. Throughout treatment, participants are asked to consider how they can employ their signature strengths to help them manage high-risk situations for smoking. For example, someone with high *Love of Learning* may be encouraged to seek out information on the health benefits of quitting smoking, whereas someone high in *Kindness* may be encouraged to use some of their money saved from not smoking to treat a friend to dinner.

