# Sample size calculations

We estimated abstinence rates in PPT-S+ by roughly averaging and rounding the abstinence rates seen in our developmental trial [18] and pilot randomized controlled trial [19]. For PPT-S+, we estimated 45%, 30%, and 25% abstinence at 12, 26, and 52 weeks, with 20% continuously abstinent. Results of the pilot study suggested differences in abstinence rates between PPT-S and ST that ranged from roughly 12% to 15% [19]. Therefore, for ST+, we estimated 30%, 17.5%, and 12.5% abstinence at 12, 26, and 52 weeks, with 8% continuously abstinent; such effects would represent a clinically meaningful effect for PPT-S+.

For the analysis of point prevalence abstinence over time, we used a covariance matrix based on our past trial [19] and a program developed for power analysis for generalized estimating equations [36] and determined that a sample size of 272 participants would be needed to achieve power of .80 given our estimated abstinence rates. For the single measure of verified continuous abstinence, 298 participants are needed for power of .80. To allow for up to 10% of participants being lost to follow-up, however, we allowed for an initial sample of 340 in order to ensure adequate statistical power for our analyses.

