We will also test whether PA moderates the effect of PPT-S+ on smoking outcome. To do this, we will add to the model testing an interaction term between PA and PPT-S+. Given a significant interaction, follow-up analyses will establish whether there is a crossing point of PA level at which PPT-S+ is not likely to be more effective than ST+. Analyses will be repeated with the CES-D total score as the moderator.

- 1. Zeger, S.L. and K.-Y. Liang, *Longitudinal data analysis for discrete and continuous outcomes*. Biometrics, 1986. **42**: p. 121-130.
- 2. Liang, K.-Y. and S.L. Zeger, *Longitudinal data analysis using generalized linear models*. Biometrika, 1986. **73**(1): p. 13-22.
- 3. Hall, S.M., et al., *Statistical analysis of randomized trials in tobacco treatment: longitudinal designs with dichotomous outcome*. Nicotine Tob Res, 2001. **3**(3): p. 193-202.
- 4. Moher, D., et al., *CONSORT 2010 explanation and elaboration: updated guidelines for reporting parallel group randomised trials.* BMJ, 2010. **340**: p. c869.
- 5. MacKinnon, D.P., et al., *A comparison of methods to test mediation and other intervening variable effects.* Psychol Methods, 2002. 7(1): p. 83-104.
- 6. Tofighi, D. and D.P. MacKinnon, *RMediation: an R package for mediation analysis confidence intervals.* Behav Res Methods, 2011. **43**(3): p. 692-700.

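### The positive-affect crossing point is sought only after a significant interaction and has no planned interval, so it will tend to fall too close to mean positive affect if the true interaction is modest

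*SAP*

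**What the plan says.** In its closing section on moderation the SAP says "we will add to the model testing an interaction term between PA and PPT-S"+, with PA measured by the CES-D positive affect subscale. The next step is conditional: "Given a significant interaction, follow-up analyses will establish whether there is a crossing point of PA level at which PPT-S+ is not likely" to beat ST+. Then, "Analyses will be repeated with the CES-D total score as the moderator".

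The SAP does not say whether the crossing point is the PA value where the fitted effect is zero or the edge of a confidence band. It plans no interval for the point, although it does plan a 95% confidence interval for the mediated effect. The significance level for the interaction is not stated.

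The Protocol (PPT-S+ section) supplies the expected direction: "In our pilot trial, the effect of PPT-S was, in fact, stronger among those with higher levels of positive affect prior to treatment". It gives no size for that interaction. Its sample size section covers point-prevalence and continuous abstinence only.

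**The concern.** With PA centred and in SD units, the fitted effect at PA value z is b_arm + b_int × z, and the crossing is at -b_arm / b_int. The interaction estimate is the denominator. If the crossing is computed only when that estimate is significant, and power for it is low, the estimates that qualify are mostly too large. A denominator that is too large pulls the crossing toward mean PA and pulls the estimated effect at the unfavourable end of PA toward zero or below.

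At stake is what the trial reports about who benefits. If the pilot's direction holds, too many low-PA smokers would appear to gain nothing from PPT-S+, and no interval would show how poorly the point is located.

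**Working it through.** **1. The plan's own figures.** For continuous abstinence, 20% against 8% at two-sided 0.05 and power 0.80 needs 131 per arm (262) without a continuity correction and 147 per arm (294) with one. The plan states 298; 298/0.9 = 332, within the 340 enrolled. For the GEE analysis the Protocol says it "determined that a sample size of 272 participants would be needed to achieve power of .80 given our estimated abstinence rates". A reconstruction with a logit link, linear time and exchangeable correlation gives 269 at a correlation of 0.6 and 304 at 0.7, so 272 corresponds to about 0.61. That correlation is inferred, since the covariance matrix is not given. Neither figure concerns the interaction.

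**2. Arm effect.** For PPT-S+, "we estimated 45%, 30%, and 25% abstinence at 12, 26, and 52 weeks, with 20% continuously abstinent"; for ST+, "we estimated 30%, 17.5%, and 12.5% abstinence at 12, 26, and 52 weeks, with 8% continuously abstinent". The log odds ratios at 12, 26 and 52 weeks are 0.65, 0.70 and 0.85. I use 0.7 at mean PA.

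**3. Standard error.** The reconstructed GEE has an effect of about 0.67. Power of 0.80 at N = 272 implies SE = 0.67/(1.96 + 0.84) = 0.239. Scaling gives 0.239 × √(272/340) = 0.214 at N = 340 and 0.239 × √(272/306) = 0.226 with 10% lost. With PA standardised and balanced across arms, the interaction per SD has about the same SE as the arm effect. I use 0.22 for both.

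**4. What significance requires.** Assuming two-sided 0.05, the estimate must exceed 1.96 × 0.22 = 0.43. With the arm estimate at its expected 0.7, no reported crossing can then lie further than 0.7/0.43 = 1.6 SD from the mean, wherever the true one is.

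**5. Size of the shift.** Put k = 1.96 - b_int/0.22. The mean interaction estimate among those significant in the expected direction is b_int + 0.22 × φ(k)/[1 - Φ(k)]. For b_int = 0.3:
- k = 0.596, φ(k) = 0.334, 1 - Φ(k) = 0.276
- mean = 0.3 + 0.22 × 1.21 = 0.57, which is 1.9 times the truth
- effect at -1 SD = 0.70 - 0.57 = 0.13, against a true 0.70 - 0.30 = 0.40

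The same steps, with the median crossing from a normal approximation, give:

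| Assumed interaction per SD | Power | True crossing (SD) | Median reported crossing (SD) | Effect at -1 SD: true | Effect at -1 SD: mean reported |
|---|---|---|---|---|---|
| 0.2 | 15% | -3.5 | -1.3 | 0.50 | 0.16 |
| 0.3 | 27% | -2.3 | -1.25 | 0.40 | 0.13 |
| 0.5 | 62% | -1.4 | -1.12 | 0.20 | 0.07 |
| 0.72 | 91% | -0.97 | -0.93 | -0.02 | -0.06 |
| 1.0 | over 99% | -0.7 | -0.7 | -0.30 | -0.30 |

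**6. Check with fitted GEE models.** Simulated trials (3,000 per setting, N = 340, arm effect 0.72, robust SE) gave true against median reported crossings of -3.6 and -1.38 at 0.2, -2.4 and -1.31 at 0.3, -1.44 and -1.18 at 0.5, -1.00 and -0.96 at 0.72, and -0.72 and -0.71 at 1.0. At 0.36 (true -2.0), the reported crossing was too close to the mean in 91% of qualifying trials. With PA roughly normal, 11% of smokers then fell on the no-benefit side, against 2% in truth. N = 306 gave the same pattern. Without the significance condition, the ratio was recovered: -2.05 for a true -2.00 and -1.45 for a true -1.44.

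**7. Interval.** A Fieller 95% interval covers 95% when computed in every trial. Among qualifying trials it covers about 84% at an interaction of 0.2, about 91% at 0.3 and about 96% at 0.5.

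**The case against.** Testing an interaction before probing levels of a moderator is a conventional guard against over-reading subgroups. It also has a technical basis, because a Fieller interval for the crossing is bounded only when the interaction is significant at the same level. Both points stand. They support keeping the test and labelling the results exploratory. They do not support reporting a crossing with no interval, or withholding the effect estimates across PA, which can be estimated whatever the p-value.

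Stronger readings are tempting, and the documents do not support them:

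- **That the crossing will be wrong.** The Protocol gives the pilot's direction but no size. At 0.72 the shift is negligible and at 1.0 there is none. At 0.5, 28% of qualifying crossings in the GEE simulation fell further from the mean than the truth.
- **That low-PA smokers are necessarily the ones affected.** This needs the pilot's sign. With no true interaction about 5% of trials qualify, and about half of those point at high-PA smokers.
- **That the plan creates a rule for withholding treatment.** The SAP asks whether a crossing exists and attaches no eligibility or treatment decision to it.
- **That PA goes unreported if the interaction is not significant.** The interaction test is unconditional and CES-D PA is a covariate in the primary model. Only the crossing-point follow-up is conditional.
- **That the significance condition causes the larger no-benefit zone seen under a confidence-band definition.** Most of that zone is there anyway: at an interaction of 0.36 the band edge is at -0.46 SD with the condition and -0.65 SD without it. The fault there would be treating non-significance as absence of benefit, and the SAP does not say that it uses that definition.

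**Conclusion.** The concern holds as a conditional tendency. The SAP states the significance condition, plans no interval for the crossing, and the trial is not sized for an interaction. If the true interaction is below about 0.5 log-odds per SD of PA (power below about 65%), the reported crossing tends to be too near mean PA, by about 0.3 SD at 0.5, 1 SD at 0.3 and 2 SD at 0.2. Benefit at the less favoured end is understated to match. At about 90% power or more the effect is negligible.

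This rests on an arm effect near 0.7, an SE near 0.22, two-sided 0.05, roughly normal PA, an exchangeable correlation near 0.6, and the crossing read as the zero of the fitted effect. The interaction sizes are assumptions. A smaller arm effect leaves the pattern in place: with 0.35 and SE 0.214, an interaction of 0.335 gives a true crossing of -1.04 SD and a median reported one of -0.62 SD.

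This is a moderation analysis. The primary test and the sample size are not affected.

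**What to change.** Keep the interaction test, and replace the conditional sentence in the SAP with the following:

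- Report the PPT-S+ versus ST+ effect across the observed range of PA with 95% confidence bands, whatever the interaction p-value. Do the same for the CES-D total score.
- Define the crossing point as the PA value where the fitted effect is zero, and give it a Fieller or bootstrap 95% confidence interval.
- Say when that interval is unbounded or the point lies outside the observed range.
- State that a region where the effect is not significant is not evidence of no benefit, and label the plot exploratory.

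The cost is about two sentences and one plot per moderator, with no new data. The price is a less definite result. Whenever the interaction is not significant, the Fieller interval for the crossing will be unbounded; at an assumed interaction of 0.3 that is about 73% of trials (100% less 27% power). If the interval is computed only in qualifying trials, it still under-covers at low power, so the bands across PA should carry the interpretation.
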